4 TRIAL DESIGN

4.1 Overall Design

This trial is a block urn randomized (by age: <80 vs. \geq 80, NIHSS score: 6-10 vs. >10, and ASPECTS: 5-7 vs. 8-10, for a total of 8 urns), blinded assessor, placebo-controlled, parallel group, two-dose (full and half), longitudinal (pre-stroke, post-treatment, 48-hour, discharge, 30-day, and 90-day) study with equal arm sample sizes (1:1:1). Although the trial's main purpose is to demonstrate safety, superiority is hypothesized over placebo and lower dose for secondary and tertiary aims.

AIS large vessel occlusion participants who are selected for EVT will be given a 48-h infusion of either 0.5 mL/kg/h RNS60 (up to a maximum of 65 mL/h), 1 mL/kg/h RNS60 (up to a maximum of 130 mL/h) or 1 mL/kg/h RNS60 (up to a maximum of 130 mL/h) of saline.

The end of the trial is defined as the date that the last enrolled participant has completed their Day 90 visit/contact.

A target of 100 male and female participants aged 18 years and older with AIS and who are selected for EVT will be enrolled.

All participants in the trial will be followed for 90 days (or until death if prior to 90 days). At Day 30 and Day 90 participants will return to clinic. If an in-clinic visit is not possible the participant, or if participant cannot be contacted or cannot communicate well, a legally authorized representative can be contacted by telemedicine (preferred) or by telephone (last option).

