4.2 Scientific Rationale for Study Design

The RNS60 trial design rationale is based on the promising design of the recently completed ESCAPE-NA1 trial¹⁰. There is a compelling need to develop neuroprotectants in order to increase the proportion of patients who may benefit from EVT and do not suffer from delays in care. Effective neuroprotectants could improve the outcomes of patients and bridge patients with AIS into candidates for endovascular or pharmacological recanalization treatment. The rapid progression of irreversible brain injury in most acute strokes implies a short window of clinical efficacy for any treatment, including RNS60.

The current trial is intended to demonstrate safety of RNS60 and, as a secondary aim, to provide first data on whether RNS60 may improve functional independence, reduce mortality, and reduce infarction volumes. As such, this trial is a block urn randomized (by age: <80 vs. \geq 80, NIHSS score: <10 vs. \geq 10, and ASPECTS: 5-7 vs. 8-10 for a total of 8 urns), blinded assessor, placebo-controlled, parallel group, two-dose (full and half), longitudinal (pre-stroke, post-treatment, 48-hour, discharge, 30-day, and 90-day) study with equal arm sample sizes (1:1:1). Although the trial's main purpose is to demonstrate safety, superiority of the higher dose is hypothesized over placebo and the lower dose (secondary and tertiary objectives).

Randomized LVO stroke patients will be given a 48-h infusion of either 0.5 mL/kg/h RNS60 (up to a maximum of 65 mL/h), 1 mL/kg/h RNS60 (up to a maximum of 130mL/h), or 1 mL/kg/h (up to a maximum of 130 mL/h) placebo (normal saline) within 30 minutes of randomization but prior to arterial access closure (the exact time to start dosing will be determined by the timing of the informed consent).

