9.3.3 Analyses of Safety and Efficacy

All efficacy results will be examined using both ITT and per protocol populations. Although the trial's main purpose is to demonstrate safety, several measures of efficacy will be examined in order to provide effect size estimates for a appropriately powered future trial demonstrating efficacy. As such, both pairwise comparisons at various timepoints and longitudinal data will be examined.

- 1) Primary efficacy outcome
- 2) Secondary efficacy outcomes, as specified in the order presented below

Outcome	Statistical Analysis Methods
Primary	All analyses will be accomplished using SAS Software 9.4 (SAS Inc. Cary, NC). Primary: The frequency of SAEs, SAEs resulting in death, AEs, and discontinuations due to AEs will be summarized as counts and percentages between conditions. Comparisons will be conducted using Fisher's Exact tests.
Secondary	
Secondary: Comparisons between conditions for mRS will be evaluated using generalized mixed modeling assuming a binomial distribution (0-6) with sandwich estimation nested by site and participant, when applicable. Pairwise comparisons of mRS will be conducted at day 90 using a Dunnett correction. In addition, simple and interaction effects between pre-stroke, discharge, 30 and 90-day mRS by condition will be examined. Because superiority over placebo and lower dose is hypothesized, testing will reflect this superiority framework with one-tailed tests.
 
Both NIHSS score and BI at Day 90 will be examined in a similar fashion assuming a binomial distribution (0-42 & 0-100) with sandwich estimation nested by site and participant (when applicable). Pairwise comparisons between conditions will be conducted at day 90 using a Dunnett correction. In addition, simple and interaction effects between pre-treatment, discharge, 30 and 90-day NIHSS scores and BI by condition will be examined. Because superiority over placebo and lower dose is hypothesized, testing will reflect this superiority framework with one-tailed tests.
 
Mortality will be examined using Kaplan-Meier estimation with pairwise comparisons with a Dunnett correction with censoring on last known follow up. Because superiority over placebo and lower dose is hypothesized, testing will reflect this superiority framework with one-tailed tests. Marginal Cox Hazard regression will also be used to evaluate mortality with sandwich estimation and nesting within site.

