2.2 Study Design

2.2.1 Overview

This trial is a Phase 2, block urn randomized, blinded assessor, placebo-controlled, parallel group, two-dose (high and low), and longitudinal (pre-stroke, post-treatment, 48-hour, discharge, and Days 30 and 90) study with equal arm sample sizes (1:1:1). All participants in the trial will be followed for 90 days (or until death if prior to 90 days). Participants are considered to have completed the study if they have remained in the study until Day 90 or they have died prior to Day 90. The end of the trial is defined as the date the last enrolled participant has completed their Day 90 visit/contact.

The trial's primary aim is to demonstrate the safety of RNS60. As a secondary aim, the study will provide first data on whether RNS60 may reduce global disability, improve neurological outcome, reduce worsening of stroke and reduce infarction volumes. Superiority of the higher dose is hypothesized over placebo and of the lower dose over placebo is hypothesized for all secondary and tertiary objectives.

AIS large vessel occlusion participants who are selected for Endovascular Thrombectomy (EVT) will be given a 48-h infusion of either 0.5 mL/kg/h RNS60 (up to a maximum of 65 mL/h), 1.0 mL/kg/h RNS60 (up to a maximum of 130 mL/h), or 1.0 mL/kg/h (up to a maximum of 130 mL/h) placebo (normal saline) starting within 30 minutes of randomization (but prior to arterial access closure).

Randomization will be done with block urn randomization to balance age (<80 vs. \geq 80), NIHSS score (6-10 vs. >10), and Alberta stroke program early computerized tomography score (ASPECTS) (5-7 vs. 8-10) for a total of 8 urns.

Table 1 shows the schedule of activities of randomized participants.

Table 1: Schedule of Activities for Randomized Participants

| Visit/Contact | V1 | V2 | V3 | V4 | V5 | V6/ End of Trial |
|---|---------------------|-------------------|--------------------------------|------------------------------------|---------------------|---------------------|
| Day | Day 0 Baseline | Day 1 Post-EVT | Day 2/or early discharge | Day 6 ¹ or discharge | Day 30 ² | Day 90 ² |
| Window | (24 h+/-4h) | | (48 h+4h) | (-5 d) | | (-21 to +7d) |
| Informed consent | X | | | | | |
| Regained capacity informed consent ³ | | | X | X | X | X |
| History and physical examination ⁴ | X | X | X | | | |
| Weight ⁵ | X | | X | | | |
| Vital Signs (BP, HR, Temperature) ⁶ | X | X | X | | | |
| Chest radiograph | X ¹² | X | X | | | |

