3.4 Safety and Efficacy Assessments

The primary safety analysis will be conducted in the Safety Population. The secondary efficacy analysis will be conducted in the ITT and PP Populations.

3.4.1 *Primary Safety Endpoints*

Frequencies and severities of SAEs

The proportion of participants with SAEs through Day 90 between the three treatment groups (RNS60 0.5 mL/kg/h, RNS60 1.0 mL/kg/h, and placebo 1.0 mL/kg/h)

In addition, the frequency and severity categories will be summarized with counts and percentages of SAEs by treatment and site and in total. See Appendix C for definition of SAE.

90-day Mortality

The proportion of participants alive at Day 90 between the three treatment groups (RNS60 0.5 mL/kg/h, RNS60 1.0 mL/kg/h, and placebo 1.0 mL/kg/h).

3.4.2 *Secondary Efficacy Endpoints*

All outcomes will be assessed in the following hierarchical order (to control of the overall Type I error rate). As it is hypothesized that higher dosage will result in less disability, subjects receiving placebo 1.0 mL/kg/h will first be compared to RNS60 1.0 mL/kg/h and then, as a lower ranking secondary endpoint, combined RNS60 doses (1.0 mL/kg/h and 0.5 mL/kg/h) compared to placebo, and finally RNS60 0.5 mL/kg/h compared to placebo. Specifically, efficacy of each of the 5 key endpoints will be assessed between high-dose RNS60 compared to placebo, followed by the same endpoints between combined RNS60 doses (1.0 mL/kg/h and 0.5 mL/kg/h) compared to placebo, finally followed by the same 5 endpoints between RNS60 low dose (0.5 mL/kg/h) compared to placebo:

1. Disability based on mRS score, high-dose vs placebo
2. Infarct progression/regression, high-dose vs placebo
3. NIHSS score, high-dose vs placebo
4. Worsening of stroke high-dose vs placebo
5. BI, high-dose vs placebo
6. Disability based on mRS score, combined-dose vs placebo
7. Infarct progression/regression, combined-dose vs placebo
8. NIHSS score, combined-dose vs placebo
9. Worsening of stroke, combined-dose vs placebo

10. BI, combined-dose vs placebo
11. Disability based on mRS score, low-dose vs placebo
12. Infarct progression/regression, low-dose vs placebo.
13. NIHSS score, low-dose vs placebo
14. Worsening of stroke, low-dose vs placebo
15. BI, low-dose vs placebo

If a comparison listed above is determined to be not statistically significant, then the remaining comparisons in the hierarchy will be tested in any case and interpreted in an exploratory manner.

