6.4 Changes from Protocol-Specified Statistical Analyses

The protocol specifies ITT population as all randomized subjects. This SAP clarifies that ITT population will include all randomized subjects who received study drug. ITT population will exclude subjects who were randomized and did not receive study drug.

There are no significant changes from protocol-specified statistical analysis apart from specifying the type of analysis to be used and further defining endpoints. The SAP will be considered as the governing document and in case of any differences between this SAP and the study protocol, the SAP will supersede the protocol.

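### The protocol hypothesizes that the higher dose beats the lower dose; the SAP names no high-versus-low efficacy contrast and does not list the change

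*SAP*

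**What the plan says.** The protocol gives the hypothesis in the synopsis (Statistical Assumptions), in 4.1, in 4.2 and in 9.3.3. Section 4.1 has "superiority is hypothesized over placebo and lower dose for secondary and tertiary aims". Section 4.2 makes clear that the higher dose is meant: "superiority of the higher dose is hypothesized over placebo and the lower dose". Section 9.3.3 turns this into a testing commitment: "Because superiority over placebo and lower dose is hypothesized, testing will reflect this superiority framework with one-tailed tests". It repeats the commitment for mRS, NIHSS and BI, mortality, imaging volumes and worsening of stroke. Its multiplicity method reads "Pairwise comparisons of mRS will be conducted at day 90 using a Dunnett correction", with no reference arm named.

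SAP 2.2.1 reads: "Superiority of the higher dose is hypothesized over placebo and of the lower dose over placebo is hypothesized for all secondary and tertiary objectives". SAP 2.1.2 and 3.4.2 set the testing order as high dose, then combined doses, then low dose, each against placebo. The reason given in 3.4.2 still presumes a dose response: "As it is hypothesized that higher dosage will result in less disability". The Wilcoxon analysis in 3.4.4.1 uses three data sets, each of them against placebo.

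SAP 6.4 names one change, the ITT definition, and then states: "There are no significant changes from protocol-specified statistical analysis apart from specifying the type of analysis to be used and further defining endpoints". It also makes the SAP override the protocol.

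**The concern.** A hypothesis that the protocol says will be tested is missing from the document that governs the analysis, and the section meant to record such changes does not mention it. Neither of the exceptions in 6.4, the type of analysis and the further definition of endpoints, describes the removal of a between-dose hypothesis.

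The protocol says the efficacy results are to provide estimates for powering a later trial. A reader of a two-dose trial will ask whether the doses differ. With only placebo contrasts named, the material to hand is two results set side by side, and a difference in significance is not evidence of a difference in effect. The combined-dose contrast averages the two doses, with no named estimate of how far apart they are.

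**Working it through.** The plan has no power or sample-size calculation, so there is no figure to reproduce. The check is a count of contrasts followed by three short calculations.

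**1. Count (SAP 3.4.2, 3.4.4.1).** Ranked tests: 5 endpoints × 3 contrasts = 15, of which 0 are high versus low. The text for mRS, infarct volume and worsening of stroke names high, low and combined, each versus placebo. Wilcoxon data sets: 3, of which 0 are high versus low.

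**2. What the two placebo effects can give.** Take equal arms of size n and variance σ² (1:1:1 allocation, SAP 2.2.1). Let H, L and P be the arm means.
- Var(H−P) = Var(L−P) = 2σ²/n. Cov(H−P, L−P) = σ²/n, from the shared placebo arm, so the correlation is 0.5.
- Correct: Var(H−L) = 2σ²/n.
- Treating the two effects as independent: 2σ²/n + 2σ²/n = 4σ²/n.
- SE ratio = √(4/2) = 1.41, so the naive interval is 41% too wide.

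**3. How often the two p-values split when the doses are the same.** Let π be the power of each dose against placebo, counting significance in the favourable direction, and let h = Φ⁻¹(π). Then P(both) = Φ₂(h, h; 0.5) and P(high only) = π − P(both). At π = 50%, P(both) = 1/4 + asin(0.5)/(2π*) = 1/3, where π* = 3.1416. The documents give no power, so π is an assumption, shown as a range:

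| Assumed power per contrast | P(both) | P(high only) |
|---|---|---|
| 10% | 0.032 | 0.068 |
| 20% | 0.087 | 0.113 |
| 50% | 0.333 | 0.167 |
| 80% | 0.687 | 0.113 |
| 90% | 0.832 | 0.068 |

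The 50% row is the maximum. Low only has the same probability as high only.

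**4. Precision of the missing estimate.** The target of 100 participants gives about 33 per arm. Assume a 50% disability rate in both dose arms.
- Half-width = 1.96 × √(2 × 0.5 × 0.5 / 33) = 0.241, or about ±24 percentage points.
- SE of the log odds ratio = √(2 / (33 × 0.25)) = 0.492, so an observed odds ratio of 1 has an interval of about 0.38 to 2.62.
- If the true rates were 50% and 40%, power would be 12.5% two-sided.

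**5. The protocol's own method.** With placebo as reference, Dunnett covers two comparisons and excludes high versus low. The one-sided 5% critical value for two comparisons is 1.916. Applied to all three directional pairs, it gives a family-wise error of about 7.2% by simulation. As written, the protocol therefore does not say how its between-dose hypothesis would be tested.

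**The case against.** A reader might infer that the trial never compares its doses. The documents do not support that. Safety is tabulated for all three arms, and the blood-pressure ANCOVA in SAP 3.5.3 presents comparisons between treatment groups without limiting the pairs. The efficacy text speaks of comparing three treatments, and LSMEANS/DIFF can output every pair. The SAS code is blacked out and part of the 24-hour NIHSS text is not visible. The supportable statement is that no high-versus-low efficacy contrast is named.

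The protocol is also not clean. Its Dunnett correction names no reference arm, and none of its listed objectives or outcomes is a dose comparison. That weakens any claim that a fully specified test was removed. The hypothesis and the commitment to test it are still in the text.

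A determined reader could recover the interval if the combined-dose contrast is reported with its own variance from the same model: Var(H−L) = 2Var(H−P) + 2Var(L−P) − 4Var(combined−P). The text for that contrast does not promise a confidence interval, and back-calculation is no substitute for a reported estimate.

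Leaving the contrast out of the ranked tests is defensible. Placebo matches the infusion rate of the high dose only, so high versus low mixes dose with infused volume. SAP 2.2.2 accepts that the lower rate may unblind infusion staff, and the precision is poor. All of this argues against a formal test, not against an exploratory estimate.

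Two further inferences go too far. No section says that a later trial's dose will be chosen by which contrast reached significance. And the protocol hypothesis covers secondary and tertiary aims, so it gives no ground for requiring between-dose contrasts for SAEs or for the primary safety analysis of 90-day mortality.

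**Conclusion.** The concern holds for efficacy. The governing SAP narrows the protocol's hypothesis, names no high-versus-low efficacy contrast, and does not record the change in 6.4, while still ordering its tests on the premise that more drug does better. The practical cost is moderate: the dose difference lacks a planned interval, and split p-values would favour the high dose by chance in about 7% to 17% of trials with identical doses. That range rests on equal arms, a normal approximation, equal true effects and assumed power between 10% and 90%. No ranked comparison against placebo is invalidated. This should be corrected before database lock.

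**What to change.** - In SAP 3.4.2, for each of the five ranked endpoints, add RNS60 1.0 versus 0.5 mL/kg/h from the same model, with estimate and 95% CI. Label it exploratory and outside the 15-step hierarchy, and say that any dose difference is read from this contrast.
- In SAP 3.4.4.1, add a fourth data set containing the high-dose and low-dose arms.
- In SAP 6.4, list the changed hypothesis and give the reason.
- Beside the new contrast, state its limits: wide intervals, dose mixed with infused volume, and possible unblinding of infusion staff in the low-dose arm.

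The cost is a few lines of text and one contrast statement per model. It needs no new data and takes no alpha from the ranked tests. If the sponsor prefers not to report the contrast, the entry in 6.4 with its reason is the minimum.

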2.2.4 Sample Size Determination

As the primary aim of this proof-of-concept study is to demonstrate safety, no power analysis was conducted for sample size determination. The trial targets to enroll a total number of 100 participants aged 18 years or older with LVO AIS and who are selected for endovascular revascularization.

Anticipated attrition factors include death from stroke unrelated to treatment (10%), discontinuation of treatment due to symptoms of fluid overload (20%), and early discharge (5%).

2.3 Study Endpoints

2.3.1 Primary Safety Endpoints

The primary safety endpoints include:

- 1) Frequencies and severities of SAEs (see Appendix C for definition of SAE).
- 2) 90-day mortality (as a proportion).

2.3.2 Secondary Efficacy Endpoints

Secondary endpoints include:

- 1) Disability based on the mRS score at Day 90 as a binary outcome (0-2, 3-6).

The mRS is a commonly used valid and reliable clinician-reported outcome measure in subjects who have suffered a stroke. It measures functional recovery (the degree of disability or dependence in daily activities in a 6-point disability scale with possible scores ranging from 0 to 5. A score of 6 is used for subjects who expire.

Table 2. Description of scores in mRS

| Score | Description |
|-------|---|
| 0 | No symptoms at all |
| 1 | No significant disability despite symptoms; able to carry out all usual duties and activities |
| 2 | Slight disability: unable to carry out all previous activities but able to look after own affairs without assistance |
| 3 | Moderate disability: requiring some help, but able to walk without assistance |
| 4 | Moderately severe disability: unable to walk without assistance and unable to attend to own bodily needs without assistance |
| 5 | Severe disability; bedridden, incontinent, requiring constant nursing care and attention |
| 6 | Death (at hospital or after discharge) |

The post-dose mRS score will be obtained at Day 6 (or discharge), and Days 30 and 90. Premorbid mRS status may be obtained at any time, but ideally at the Day 1 or 2 visit. The mRS will only be scored by those trained and certified in the use of this scale.

- 2) Infarct volume of stroke at 48h.

Infarct progression/regression as measured by MRI of the brain in RNS60 versus placebo control participants will be calculated from the 48h imaging and compared to the

immediate post-thrombectomy MRI. The volume of injured tissue on Fluid Attenuated Inversion Recovery (FLAIR) and T2 weighted images will be compared.

3) NIHSS score at hour 24.

The NIHSS is a standardized neurological examination scale that is a valid and reliable measure of disability and recovery after acute stroke. The NIHSS assessment is a standardized 15-item impairment scale, intended to evaluate neurologic outcome and degrees of recovery for subjects with stroke. The scale assesses levels of consciousness, extraocular movements, visual fields, facial muscle function, extremity strength, sensory function, coordination (ataxia), language (aphasia), speech (dysarthria), and hemi-inattention (neglect). The NIHSS will be administered at baseline, post-EVT (2h), 24h, 48h, Day 6 (or discharge), Day 30 and Day 90. The NIHSS will only be scored by those trained in the use of this scale.

Table 3. Scales and score range in NIHSS

| Item | Scales | Score range |
|------|----------------------------|-------------|
| 1a | Level of Consciousness | 0-3 |
| 1b | LOC Questions | 0-2 |
| 1c | LOC Commands | 0-2 |
| 2 | Best Gaze | 0-2 |
| 3 | Visual | 0-3 |
| 4 | Facial Palsy | 0-3 |
| 5a | Motor Arm –Left Arm | 0-4 |
| 5b | Motor Arm –Right Arm | 0-4 |
| 6a | Motor Leg –Left Leg | 0-4 |
| 6b | Motor Leg – Right Leg | 0-4 |
| 7 | Limb Ataxia | 0-2 |
| 8 | Sensory | 0-2 |
| 9 | Best Language | 0-3 |
| 10 | Dysarthria | 0-2 |
| 11 | Extinction and Inattention | 0-2 |

Scoring:

Each item is scored in the respective ranges listed in Table 3 (0-2, 0-3, or 0-4), and untestable items are scored as "UN". A score of 0 indicates normal performance. Total scores on the NIHSS range from 0-42, with higher values reflecting increasing severity.

Stroke severity is further stratified in the following way (Brott, Adams, Olinger, Marler, Barsan, Biller, & Hertzberg, 1989):

> 25: Very severe

15-24: Severe

5-14: Mild to moderately severe

< 5: Mild

The predictive value of the scale can also aid in planning a subject's rehabilitation or long-term care needs as early as on the day of admission. NIHSS scores can be

interpreted in the following way (Schlegel, D., Kolb, S. J., Luciano, J. M., Tovar, J. M., Cucchiara, B. L., Liebeskind, D. S., & Kasner S. E., 2003):

≥ 14 – Severe: Long-term care in nursing facility required

6-13 – adequate: Acute inpatient rehabilitation required

≤ 5 – Mild: 80% with this score are discharged home

4) The proportion of study subjects with worsening of stroke at the 90-day study period.

Worsening of stroke is defined as progression, or hemorrhagic transformation of the index stroke, as documented by brain imaging, which is (a) life-threatening requiring intervention and/or (b) results in increased disability as gauged by a ≥ 4-point increase from lowest National Institutes of Health Stroke Scale (NIHSS) pre decline and/or (c) results in death.

5) Barthel Index at Day 90.

The BI is an index of functional independence. Its values range from 0 to 100, with higher scores indicating greater independence.

Table 4. Scales and score range in BI

| Item | Score range |
|-----------------------------------|-------------|
| Feeding | 0-10 |
| Bathing | 0-5 |
| Grooming | 0-5 |
| Dressing | 0-10 |
| Bowels | 0-10 |
| Bladder | 0-10 |
| Toilet use | 0-10 |
| Transfers (bed to chair and back) | 0-15 |
| Mobility (on level surfaces) | 0-15 |
| Stairs | 0-10 |

Item scores vary in increments of 5 points.

6) Health-related quality of life, as measured by the EuroQol health-related quality of life (EQ-5D-5L) at Day 90.

EQ-5D-5L is developed by EuroQol Research Foundation and is a generic instrument for measuring and describing health-related quality of life.

It consists of two elements, a 5-item questionnaire and an EQ-Visual Analogue Scale (VAS). Both elements are interviewer administered by study staff.

EQ-5D-5L is a version that further improves the sensitivity of EQ-5D-3L, provides respondents with a wider range of options to describe their health and is comprised of five response levels to five different dimensions.

- **5-Item Questionnaire:** The questionnaire provides a simple descriptive profile of health state. The questionnaire comprises 5 dimensions (mobility, self-care, usual activities, pain/discomfort, anxiety/depression) and each dimension has 5 response levels (1-no problems, 2-slight problems, 3-moderate problems, 4-severe problems,

5-unable to/extreme problems). The resulting 5-digit code corresponds to the response of each dimension of the health state. For instance, 11111 and 55555 indicate the best health condition and the worst health condition, respectively.

- **Index Score:** The health state is summarized to be a single number, EQ-5D-5L Index score, by applying standard value set. A representative sample of the general population in a country/region is asked to place a value on health states and the standard value set is developed. The standard value set varies by country and reflects what health state is regarded as good according to country-specific preferences. Refer to the paper written by Pickard and his colleagues (2019) for the U.S. standard value set.

EQ-Visual Analogue Scale (VAS): EQ-VAS provides an alternative way to measure subjects' perception about their overall current health. The subject is asked to mark X on the scale to indicate how their health is 'TODAY'. This scale consists of numbers from 0 (the worst health you can imagine) to 100 (the best health).

